1 PROTOCOL SUMMARY

1.1 SYNOPSIS

Title:	Adalimumab in Juvenile Idiopathic Arthritis-associated Uveitis Stopping Trial (ADJUST)
Study Description:	Multicenter, block-randomized, double-masked, placebo-controlled trial to compare the safety and efficacy of stopping adalimumab treatment versus continuing adalimumab treatment in patients with uveitis associated with juvenile idiopathic arthritis (JIA) or patients with chronic anterior uveitis (CAU). 118 patients with JIA-associated uveitis or CAU, with control of ocular inflammation on adalimumab will be randomized to either continue adalimumab at their current dose or stop adalimumab. Patients will complete monthly visits for 4 months in addition to visits at 6, 8, 10, and 12 months.
Objectives:	Primary Objective: To compare time to recurrence of ocular inflammation between patients with JIA-associated uveitis or CAU, randomized to stop adalimumab treatment and patients randomized to continue treatment. Secondary Objectives: To determine predictors of JIA-associated uveitis or CAU disease recurrence. To compare 6- and 12-month outcomes between the two treatment groups.
Endpoints:	Primary Endpoint: Time to treatment failure, up to 12 months post-randomization.

[figure not shown]
Study Population:	118 patients ≥2 years of age in the U.S., UK, and Australia, with a history of JIA-associated uveitis or chronic anterior uveitis. Original diagnosis must have been made prior to 16 years of age (but patients can be >16 at time of enrollment). Patients must have achieved steroid-sparing control of ocular inflammation and inactive arthritis on adalimumab or a biosimilar of adalimumab for ≥12 consecutive months. Patients may not have used systemic corticosteroid or ocular corticosteroid injection within the last 180 days and must be on ≤2 drops daily of 1% prednisolone acetate with stable dose for ≥90 days. The dose of adalimumab must be stable for ≥180 days and should be no greater than 40mg biweekly for patients ≥30kg and 20mg biweekly for patients <30kg. If on a concomitant antimetabolite, dose must be stable for ≥90 days and ≤25mg weekly for methotrexate, ≤3g daily for mycophenolate mofetil, ≤250 mg daily for azathioprine, or ≤ 20 mg daily for leflunomide.
Phase:	IV
Enrollment Centers:	10 centers in the U.S., 9 in the UK, and 1 in Australia. Additional sites may be added during the study to facilitate enrollment.
Description of Study Intervention:	Adalimumab administered subcutaneously or placebo administered subcutaneously. Patients randomized to continue adalimumab will remain on the same dosage at which they entered the trial. Standard dosages in clinical practice are 40mg every other week for patients ≥30kg and 20mg every other week for patients <30kg. The volume-matched placebo will be administered every other week. If on methotrexate or mycophenolate mofetil, patients will continue their same dose during the trial.
Study Duration:	Anticipated project duration of five years with enrollment starting in March 2020 and completion of analysis and publication by December 2025.
Participant Duration:	Each individual participant will complete all study assessments during a 48-week period.

1.2 SCHEMA

Prior to Enrollment

Total 118: Obtain informed consent. Screen potential participants by inclusion and exclusion criteria; obtain history, document.

Visit 1
Baseline

Follow monthly through Month 4

Follow-up assessments and medication dispensing.
Refer to **Section 1.3, Schedule of Activities**

Months 6, 8, and 10

Follow-up assessments and medication dispensing.
Refer to **Section 1.3, Schedule of Activities**

Treatment Failure or Month 12 (whichever occurs first)

Primary outcome assessments of primary study endpoints.
Refer to **Section 1.3, Schedule of Activities**

1.3 SCHEDULE OF ACTIVITIES (SOA)

Visit Schedule

Visit	Code	Week *	Window (weeks)
Baseline	BL	0	
Month 1	M1	4	2 - 6
Month 2	M2	8	>6 - 10
Month 3	M3	12	>10 - 14
Month 4	M4	16	>14 - 18
Month 6	M6	24	>22 - 26
Month 8	M8	32	>30 - 34
Month 10	M10	40	>38 - 42
Month 12	M12	48	>46 - 50
AE check phone call	Other	58	>56 - 60

* since baseline / first treatment administration

Study Visit Assessment Schedule

	Baseline ^a	Months 1-4	Month 6	Months 8 & 10	Month 12	Treatment Failure ^b	Additional Visit ^c
Informed consent	✓						
Confirmation of eligibility criteria	✓						
Medical history and demographic data collection	✓						
Complete ophthalmic exam	✓	✓	✓	✓	✓	✓	✓
Visual acuity	✓	✓	✓	✓	✓	✓	✓
OCT	✓	✓	✓	✓	✓	✓	✓
Serum chemistry and complete blood count	✓	Month 3 ^d	✓	Month 8 or 10 ^d	✓	✓ ^e	✓ ^c
MRP8/14 serum levels	✓		✓		✓	✓	
Anti-adalimumab antibody levels	✓		✓		✓	✓	
Blood draw for biobanking	✓		✓		✓	✓	
Rectal swab	✓				✓	✓	
Pregnancy test for women of reproductive age	✓	✓	✓	✓	✓		✓
Monitoring for arthritis activity	✓	Month 3	✓		✓	✓ ^e	
Review of AEs ^f	✓	✓	✓	✓	✓	✓	✓
Quality-of-life questionnaires	✓		✓		✓	✓	
Medication dispensing	✓	✓	✓	✓		(✓) ^g	
Review of treatment adherence and concomitant therapy		✓	✓	✓	✓	✓	✓

^aAll baseline data must be collected at or within 14 days from the date of consent, with the exception of laboratory measurements.

The baseline laboratory measurements may be collected no more than 30 days prior or up to 14 days after the date of consent.

Baseline data are encouraged to be collected on the date of the Baseline visit, which is when the patient is randomized.

^bNote that treatment failure can occur at any time, including an unscheduled visit.

^c90-day follow-up visit is necessary for patients who experience a late treatment failure where there is < 90 days of follow-up remaining in the regular follow-up period. Patient will need standard of care labs if they are on an antimetabolite and if more than 90 days have passed since their last standard of care labs.

^dStandard of care labs should be checked every 3 months for patients on antimetabolites (Baseline, Month 3, Month 6, on or any time between Month 8 and Month 10, Month 12, and Treatment Failure if it occurs), and every 6 months for patients not on antimetabolites (Baseline, Month 6, Month 12, and Treatment Failure if it occurs).

^eAssessment does not need to be re-performed if done within 14 days prior to the patient's treatment failure visit.

^fAdverse Event (AE) check phone call: Patients are contacted approximately 70 days after their last study visit. Only the AE form is completed.

^gPatients randomized to continue adalimumab and patients randomized to stop adalimumab who have a treatment failure and restart will be provided open-label drug until Month 12 (or Month 15 if treatment failure occurs at Month 12).

Form Completion Schedule

After completing each study visit, study coordinators will review the electronic case report forms for completion and accuracy and submit them electronically via REDCap. If study visit data are recorded on hard copies of the forms, these paper copies should be scanned and emailed to the Coordinating Center ([contact]) and kept in a secure location at the site. All US centers are part of the Childhood Arthritis and Rheumatology Research Alliance (CARRA) and submit data to the registry for their JIA patients. As we are collecting similar data on an overlapping patient population, CARRA has allowed us to use their data collection forms. We will collect data using forms developed specifically for ADJUST in addition to several forms from the CARRA registry that are applicable to the study procedures and data collected for this study.

	Baseline	Months 1-4	Month 6	Months 8 & 10	Month 12	Treatment Failure ^a	Additional Visit ^b
Patient Consent Forms	✓						
Eligibility and Screening Form	✓						
Baseline Treatment Assessment Form	✓						
Baseline Demographics Form	✓						
Baseline Ophthalmology Form	✓						
Baseline Rheumatology Form	✓						
Clinical Eye Exam Form	✓	✓	✓	✓	✓	✓	✓
Arthritis Evaluation Form	✓	Month 3	✓		✓	✓	
Visual Acuity Form	✓	✓	✓	✓	✓	✓	✓
OCT Form	✓	✓	✓	✓	✓	✓	✓
Standard of Care Lab Form	✓	Month 3 ^c	✓	Month 8 or 10 ^c	✓	✓	✓ ^b
Research Sample Lab Form	✓		✓		✓	✓	
Adverse Event Checklist	✓	✓	✓	✓	✓	✓	✓ ^d
Quality-of-Life Questionnaires (CHAQ, CVFQ, EYE-Q, EQ-5D-Y)	✓		✓		✓	✓	
Treatment Assessment Form ^e	✓	✓	✓	✓	✓	✓	✓
Medication Adherence Log	✓	✓	✓	✓	✓	✓	✓
Patient Dropout Form (if applicable)		(✓)	(✓)	(✓)	(✓)	(✓)	(✓)

Serious Adverse Event Narrative Form (if applicable)		(✓)	(✓)	(✓)	(✓)	(✓)	(✓)
Protocol Deviation Form (if applicable)	(✓)	(✓)	(✓)	(✓)	(✓)	(✓)	(✓)
Interim Masking Decision Form (if applicable) ^f		(✓)	(✓)	(✓)			(✓)

^aTreatment failure can be declared at any visit, including an unscheduled visit.

^b90-day follow-up visit is necessary for patients who experience a late treatment failure where there is < 90 days of follow-up remaining in the regular follow-up period. Patient will need standard of care labs if they are on an antimetabolite and if more than 90 days have passed since their last standard of care labs.

^cThis form should be completed when standard of care labs are checked. For patients not on antimetabolites, this means Baseline, Month 6, Treatment Failure if it occurs, and Month 12. For patients on antimetabolites, standard of care labs should also be checked at Month 3, and at or any time between Month 8 and Month 10 visits.

^dWill also be completed at the AE check phone call, approximately 70 days after the last study visit.

^eIf the patient did not experience Treatment Failure prior to February 14, 2024, the Follow-Up Treatment Assessment form should be completed at all visits going forward, regardless of if/when the patient is later unmasked. If the patient had already experienced treatment failure prior to February 14, 2024, the Unmasked Treatment Assessment form is sufficient for all future visits.

^fTo be completed at the next study visit after February 14, 2024, if the patient had not already been unmasked due to Treatment Failure.

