While methotrexate is the mainstay of long-term, immunomodulatory therapy for JIA-associated uveitis and CAU, previous studies have shown that anywhere from 15-50% of affected children will have refractory uveitis despite adherence to methotrexate treatment.¹⁰⁻¹³ Both human and animal models have suggested the pro-inflammatory cytokine TNF- α may play a role in both JIA and uveitis pathogeneses.¹⁴⁻¹⁶ Given its demonstrated efficacy in clinical trials, adalimumab has been approved by the U.S. Food and Drug Administration (FDA) for the treatment of both JIA and non-infectious intermediate, posterior, and panuveitis.¹⁷ Adalimumab has also been shown to effectively control inflammation in more than 80% of JIA-associated anterior uveitis cases, leading to its approval for use for this indication within the National Health System (NHS) in the UK.^{18,19}

Despite strong evidence for adalimumab's short-term efficacy for treating JIA-associated uveitis and CAU, there is a lack of evidence regarding long-term treatment outcomes for such patients.^{2,3,18-24} There is some evidence to suggest that patients on adalimumab may have higher rates of adverse events compared to patients on methotrexate alone.²⁵ In addition, anti-TNF- α therapy may harbor a risk of malignancy and opportunistic infection.²⁶⁻³⁴ These health concerns contribute to a growing interest in the possible cessation of adalimumab after a patient with JIA-associated uveitis or CAU has achieved disease control.

Anti-TNF- α therapy is expensive to the patient and healthcare system.^{35,36} A single dose of adalimumab costs £350 under NHS England.³⁶ A 2013 study found that, on average, a person with health insurance coverage in the U.S. pays \$26,537 for adalimumab in the first year of treatment.³⁷ Some patients may lose coverage for the drug, which may cause them to stop treatment for financial reasons. For example, the NHS England interim policy on anti-TNF- α treatment for pediatric uveitis mandates stopping treatment after 18 months and will discontinue financial coverage of adalimumab after this time.³⁸

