Patients in the placebo arm will be encouraged to restart adalimumab. The date of treatment failure is defined as the date of the initial visit when the ocular inflammation reached the threshold. A minimum of 90 days of follow-up is required following treatment failure, so if treatment failure is declared with fewer than 90 days remaining in the 12-month follow-up period, follow-up may be extended to up to 15 months. Regardless of the course of treatment pursued after treatment failure, all patients will be followed through Month 12 or a minimum of 90 days, whichever is longer.

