4.4 END OF STUDY DEFINITION

Participants are considered to have completed the study when they complete the Month 12 visit or the last scheduled procedure for the Month 12 visit as shown in the Schedule of Activities (SoA), **Section 1.3**. The end of the study is defined as completion of the last patient's visit or procedure shown in the SoA. Note that if inflammation is increased at Month 12 to a treatment failure criterion threshold, a follow-up visit must be conducted to determine whether the treatment failure criteria are met or not. If treatment failure is declared with fewer than 90 days remaining in follow-up, patients will be followed beyond Month 12 so that all patients have a minimum 90 days of follow-up after treatment failure. There will be a 90-day post-treatment failure study visit where the Clinical Eye Exam, Visual Acuity, OCT, and Adverse Event Report will need to be completed in addition to the Month 12 study visit. Standard of care labs will also be drawn only if the patient is on an antimetabolite and if more than 90 days have passed since their last standard of care lab draw. Follow-up could be extended up to 15 months if there is late treatment failure.

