6 STUDY INTERVENTION

6.1 STUDY INTERVENTION(S) ADMINISTRATION

6.1.1 STUDY INTERVENTION DESCRIPTION

Patients randomized to continue adalimumab will receive the standard clinical practice weight-based dose of adalimumab. The dosage and route of administration is self-administration of adalimumab subcutaneously at a dose of 40mg every other week for patients $\geq 30\text{kg}$ and 20mg every other week for patients $< 30\text{kg}$, which is in accordance with standard clinical practice and its FDA approved indication for treatment of JIA.¹⁷ Further detail on justification of dosing is provided in **Section 4.3**.

Patients randomized to stop adalimumab will receive placebo treatment. The volume-matched placebo will be administered subcutaneously for masking purposes every other week.

Adalimumab is commercially available in the U.S. for treatment of polyarticular JIA and non-infectious intermediate, posterior, and panuveitis in children 2 years of age and older at the aforementioned doses. Adalimumab is commercially available in the UK for treatment of both polyarticular and oligoarticular JIA in addition to chronic, pediatric anterior uveitis at the aforementioned doses. Adalimumab is commercially available in Australia for treatment of JIA and CAU at the aforementioned doses, with an exception of patients weighing less than 15kg receive 10mg every other week. Given that the use of adalimumab in patients with oligoarticular JIA and anterior uveitis is technically off-label, the Coordinating Center has obtained an Investigational New Drug Approval from the FDA.

The US formula of adalimumab has recently been changed to be citrate-free, which is the same formula that is in use in the UK. Following this announcement, AbbVie will be providing citrate-free adalimumab and placebo to all clinical study centers.⁶³⁻⁶⁵ To ensure the participants remain completely masked to treatment, the study will provide treatment kits to patients in both arms to standardize the appearance and labeling of adalimumab and the placebo.

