6.1.2 DOSING AND ADMINISTRATION

The participant's dose will be selected based on their current weight at the time of randomization. For example, a patient weighing less than 30kg who is randomized to continue adalimumab treatment will receive a dose of 20mg every other week for up to 12 months. If a patient's weight increases during the trial, the patient must hold the larger weight for two consecutive visits (≥ 28 days apart) before receiving the higher dose of adalimumab (i.e. 40mg biweekly).

Participants randomized to receive placebo treatment will receive a volume-matched placebo dose subcutaneously every other week for up to 12 months.

Patients will take their first dose of study treatment 14 days after their most recent injection prior to entering the trial. Patients in either arm may discontinue treatment at any time for safety, intolerance, or efficacy. Further information on safety, intolerance, and efficacy definitions are provided in **Section 7.1**. After discontinuing treatment, such patients would be treated per best medical judgement and continue to be followed in the study until the completion of the Month 12 visit. If treatment failure is declared with fewer than 90 days left in the 12-month follow-up period, follow-up should be extended up to 15 months. Patients in the placebo arm may restart adalimumab during the study. Patients in the adalimumab arm may continue on adalimumab. The study will provide open-label adalimumab treatment for all patients who restart, regardless of their randomization arm. The advised dose for

restarting adalimumab will be 40mg every other week for patients $\geq 30\text{kg}$ or 20mg every other week for patients $< 30\text{kg}$.

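### Open-label adalimumab is dated to end at Month 12 for most late failures, although every late failure is followed for 90 days and other sections promise drug without that limit

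*Protocol*

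**What the plan says.** **Supply.** Protocol 1.3, footnote g, states that patients who fail and take open-label drug "will be provided open-label drug until Month 12 (or Month 15 if treatment failure occurs at Month 12"). The medication dispensing row of the same schedule has no entry at Month 12 or at the additional (90-day) visit. SAP 3.7, on patients already enrolled when enrollment stops for efficacy, also ends study-provided medication at Month 12 and mentions no extension.

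Three other protocol sections give no month:
- Section 6.1.2: "The study will provide open-label adalimumab treatment for all patients who restart, regardless of their randomization arm".
- Section 6.2.1 says that study treatments will be supplied for as long as the trial lasts.
- Section 6.5.1 promises open-label drug, within the trial, to all who have a recurrence and want to restart or continue.

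**Follow-up.** Footnote c of 1.3 says that a 90-day "follow-up visit is necessary for patients who experience a late treatment failure where there is < 90 days of follow-up remaining". Section 4.4 agrees: "If treatment failure is declared with fewer than 90 days remaining in follow-up, patients will be followed beyond Month 12". Section 3.1, repeated in 7.1, says that whatever treatment is chosen after failure, "all patients will be followed through Month 12 or a minimum of 90 days, whichever is longer". On dating: "The date of treatment failure is defined as the date of the initial visit when the ocular inflammation reached the threshold".

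**The concern.** The exception in footnote g names one visit, Month 12. The follow-up rule covers every failure with fewer than 90 days left, including failures at Month 10 and at unscheduled visits between about week 35 and Month 12. Those patients are inside the extended follow-up but outside the supply exception. The order is also odd: a Month 10 failure gets a shorter dated supply after failure than a Month 12 failure, and no reason is given.

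What is at stake is continuity of treatment in patients, mostly children, who have just flared. Section 3.1 encourages placebo-arm failures to restart adalimumab. Section 2.2 warns that patients may lose coverage, and cites an interim UK policy that "mandates stopping treatment after 18 months and will discontinue financial coverage of adalimumab after this time". An outside source is therefore likely but not assured.

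**Working it through.** **Inputs.** Month 8 = week 32, Month 10 = week 40 (window >38 to 42) and Month 12 = week 48 (window >46 to 50), all from Protocol 1.3. Minimum follow-up after failure is 90 days, counted from the initial threshold visit (3.1). Restart dosing is every other week (6.1.2). A kit holds two syringes (6.2.2). The planning medians are 10 weeks (stop) and 20 weeks (continue), with 59 per arm and 10% loss to follow-up (SAP 3.3.1).

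**Reproducing the plan's own date.** 90 days = 90/7 = 12.86 weeks. A failure at week 48 has its 90-day visit at 48 + 12.86 = week 60.86. On the schedule's four-week months, Month 15 is week 60. The Month 12 exception therefore matches the 90-day follow-up almost exactly.

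**Who needs extended follow-up.** 48 − 12.86 = 35.14, so every failure after about week 35.1.

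**Gap for a Month 10 failure.** 90-day visit: 40 + 12.86 = week 52.86. Dated supply ends at week 48. Gap: 52.86 − 48 = 4.86 weeks (34 days). If the week 48 dose is supplied, the uncovered doses are those of weeks 50 and 52. The first falls due 52.86 − 50 = 2.86 weeks before the visit.

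**Range.**

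| Case | Gap (weeks) | Uncovered doses |
|---|---|---|
| Failure week 38, Month 12 visit week 50 | 38 + 12.86 − 50 = 0.86 | 0 |
| Failure week 40, Month 12 visit week 48 | 4.86 | 2 |
| Failure week 42, Month 12 visit week 46 | 42 + 12.86 − 46 = 8.86 | 4 |
| Unscheduled failure near week 46, Month 12 at week 48 | 46 + 12.86 − 48 = 10.86 | 5 |

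A failure after week 46 falls inside the Month 12 window and could count as a Month 12 failure. If it does not, the gap approaches 12.9 weeks and 6 doses (weeks 50 to 60). Five or six doses are 3 kits either way.

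**Length of dated supply after failure.** Month 10: 48 − 40 = 8 weeks. Month 12: 60 − 48 = 12 weeks. If failure is declared 28 days after the threshold visit, these become 4 and 8 weeks.

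**How many patients.** With exponential failure times, S(t) = 2^(−t/median). The proportion first seen failing at Month 10 is S(32) − S(40).
- Stop arm: 0.1088 − 0.0625 = 0.0463; × 59 = 2.7.
- Continue arm: 0.3299 − 0.2500 = 0.0799; × 59 = 4.7.
- Together 7.4; after 10% loss, 7.4 × 0.9 = 6.7.

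**Lower scenario (an assumption).** Suppose 90% of the continue arm is still inactive at week 54, the adult open-label figure quoted in SAP 3.3.1. The weekly rate is −ln(0.9)/54, and the continue-arm proportion is 0.0146; × 59 = 0.9. The total is then 3.6, or 3.2 after 10% loss.

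**The case against.** The strongest reply is that the protocol does not clearly deny these patients drug. Section 6.2.1 promises supply for the life of the trial. Section 6.1.2 states the extension of follow-up to 15 months and, a few sentences later, promises open-label drug to everyone who restarts. Section 4.4 ends the study at the last visit on the schedule, which includes the 90-day visit. This stands, and it makes the problem a conflict between sections. It does not remove it: 4.4 also calls a participant complete at Month 12, SAP 3.7 stops at Month 12, and footnote g is the only protocol text that puts a date on supply.

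A second reply is that observation and supply are separate. The 90 days apply whatever treatment is chosen, and the Month 12 exception has an obvious purpose, since without it a Month 12 failure would get no open-label drug. That is fair. Still, the Month 15 date tracks the 90-day visit, which suggests that supply was meant to follow it.

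A third reply concerns access and numbers. Every patient entered after at least 12 months on adalimumab or a biosimilar (5.1), and Section 6.1.1 says "Adalimumab is commercially available in the UK for treatment of both polyarticular and oligoarticular JIA in addition to chronic, pediatric anterior uveitis". The 4.7 continue-arm patients failed on adalimumab, and 6.5.1 lets them switch to another drug. The SAP calls their 20-week median conservative, and its revision history reports a treatment effect much larger than planned. All of this stands. The group expected to restart is the stop arm, about 2.7 patients.

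A reader might infer that patients who flare late lose treatment, or go untreated for the whole 4.9 weeks. The documents support neither. Care after failure is at the investigator's discretion, commercial drug may fill the gap, and a week 48 dose covers to week 50. What sites actually dispensed depends on the Manual of Operations and the supply contract, which are not available here.

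**Conclusion.** The inconsistency is real and minor. On the literal reading of footnote g, a Month 10 failure is left with two doses of uncovered study supply before a visit that the protocol requires. This rests on nominal visit weeks, on failure dated at the threshold visit, and on the week 48 dose being supplied. If the 90 days ran from declaration 7 or 28 days later, the gap would be 5.86 or 8.86 weeks.

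On the SAP medians it would touch about 2.7 stop-arm patients, plus up to 4.7 continue-arm patients who stay on adalimumab. Those figures assume the planned 118. Actual numbers are lower because enrollment stopped on 14 February 2024 (Protocol 10.1.12.5).

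A reader might also infer a threat to the trial's results. There is none for the primary endpoint, power, the Month 6 and Month 12 outcomes, or time to sustained control, because none of them uses the 90-day visit. The time-to-initial-control analysis added in SAP 3.1.3 states no Month 12 cut-off, so a few late-failure observations there could be made after study supply has ended. No effect on it is shown.

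**What to change.** Reword footnote g so that open-label adalimumab is supplied until Month 12 or 90 days after treatment failure, whichever is later, for any failure in which the patient restarts or continues adalimumab. Align the Month 12 limit in SAP 3.7. A separate dispensing entry at Month 12 is optional, because footnote g already dispenses through the Treatment Failure column.

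The cost is one footnote, one SAP phrase, and about two doses (one two-syringe kit) per Month 10 failure, with at most about 3 kits for any patient. On the planned 118, Month 10 failures would need roughly 2 × 2.7 = 5 doses if only stop-arm patients take study drug, and 2 × 7.4 = 15 if all do. Masking is not affected, since patients are unmasked at failure.
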